4.0 Enrollment/Randomization

Participants will be enrolled at Aminu Kano Teaching Hospital (AKTH), Kano, Nigeria. All HIV-positive ART-experienced (≥6 months on ART) individuals found to meet the inclusion criteria will be approached by a study coordinator for enrollment into this study. The study coordinator will describe the purpose of the study and the included activities and will review the informed consent with the potential participant. Those who provide written informed consent will be enrolled.

Aim 2 will be a randomized double-blind (both participants and study physicians involved in the conduct of this study), placebo-controlled study to minimize crossovers and bias in the classification of outcomes and potential adverse effects secondary to ACE-inhibitor therapy (lisinopril), which we anticipate will be minimal. We will apply block randomization to ensure balance of baseline uACR between randomization arms. Using this block randomization, stratifying patients at time of study enrollment, we plan to enroll equal numbers of patients in each stratum.

5.0 Study Procedures

Aim 1 Study Procedures

Each consenting patient will have a full medical evaluation and will provide two firstmorning void urine specimens (5 mL) because of variability. We will measure urinary albumin and creatinine levels to calculate a mean (2 sample) uACR value. The second first-morning uACR will be obtained 4-8 weeks after the first specimen. Assays will be performed using the Roche Hitachi Cobas C 311 (Roche Diagnostics Indianapolis, IN) system, using pyrogallol red urine creatinine by a kinetic Jaffe method and urine albumin by immunoturbidimetry.^{121,122} Each consenting patient will also provide one blood sample for serum creatinine and cystatin C, from which we will calculate eGFR using the CKD epidemiology collaboration (CKD-EPI-Cr-CyC)^{123,124} equation. NOTE: We will use both serum cvstatin C¹²⁵ and CKD-EPI^{123,124} to calculate eGFR. Although the CKD-EPI equation is preferred/more accurate, Shlipak et al.¹²⁵ have shown that the use of both serum cystatin C and serum creatinine for eGFR estimations strengthens the association between eGFR and the risk of ESKD and death across diverse populations. During their first AKTH clinic visit, all screened patients will have their confirmatory HIV-1 ELISA test result as well as the most recent CD4+ count and viral load results obtained from their medical records/charts, per existing standard-of-care. Each screened patient will be given a unique study ID number, which the study team will maintain. The study ID can be linked back to individual patients (and will therefore be kept in a locked cabinet - all information linking patients to ID numbers will be destroyed once study follow-up for Aims 1-3 is complete). Individual patient data that will be collected and maintained by de-identified study ID include: age, race/ethnicity, sex, weight, BMI, and comorbid medical conditions (prior/current opportunistic infections, syphilis, cancer, hypertension, other cardiovascular diseases).

Genetics specimen collection and analysis: From all consenting patients, peripheral blood will be collected in one 10 mL EDTA vacutainer tube. Blood will be processed for buffy coat and whole blood, and will be aliquoted into multiple separate 1.0- and 2.0-mL vials (following the SOP for processing DNA blood specimens in [name] laboratory) for and stored at -80 C. DNA (buffy coat and whole blood) specimens will be stored and shipped in batches to [name] laboratory for DNA extraction using Qiagen extraction kits and genetic testing of *APOL1* risk variants. Genotyping will be performed to identify the genetic correlates of risk for kidney and potentially other end organ complications.^{17,38,126}. Genotyping will be done using TaqMan assays (San Diego,

CA) targeting the 3 chromosome 22 APOL1 variants (rs73885319 [G1], rs60910145 [G1], and rs 71785313 [G2]) associated with CKD and HIV-associated kidney disease. The APOL1 risk alleles are defined by the G1 haplotypes (rs73885319-G/rs60910145-G and rs73885319-G/rs60910145-T) and by the G2 haplotype (rs71785313-deletion). We will infer the APOL1 genotype from the number of risk alleles: individuals exhibiting two risk alleles (G1/G1, G1/G2, or G2/G2) will be assigned to the "high-risk (HR)" group, while individuals carrying no or one risk allele (G0/G0, G0/G1, and G0/G2) will be attributed to the "low-risk (LR)" group. We will also examine the risk allele groups in a categorical manner (0 vs. 1 vs. 2 alleles and 0 vs. 1 risk alleles) to determine whether presence of a single risk allele poses increased risk. We will then determine the overall prevalence of APOL1 risk alleles, including odds ratios for baseline CKD and albuminuria, and the standard error for beta comparing levels of microalbuminuria and eGFR stratified by genotype (including testing for association between the APOL1 genotype and longitudinal eGFR slope using linear regressions). In addition, we will perform crude and adjusted linear regression analyses (modified Poisson regression) to test for associations with mean uACR, eGFR, and CKD, adjusting for sex, blood pressure, and age. Based on previous genetic association work in HIVAN, we will test both additive and recessive genetic models to capture all potential risk alleles associated with microalbuminuria and CKD. Because of the strong associations reported for APOL1 with HIVAN (OR=29, U.S. and OR 89, South African, recessive model), our cohort exhibits substantial power to detect the effects of APOL1 in the recessive model. For APOL1, we anticipate that 12% of controls and 36% of cases will carry the APOL1 HR genotype; this is a strong epidemiological association, but modest on the scale of known effects of APOL1 risk alleles on kidney disease.

NOTE: We also plan to collect and store plasma, sera, and urine specimens from all screened / consenting aim 1 study participants for future analyses that we will perform by obtaining separate/additional grant funding; specifically storing specimens (-80°C) for future biomarker association and other relevant translational studies, and as a backup DNA source for quality control. We will also seek ancillary/supplemental funding to conduct 12- and 24-month follow-up of consenting Aim 1 patients for Aim 3 outcomes.

Aim 2 Study Procedures

Study Medication: Participants in the intervention arm will be given lisinopril at a starting dose of 5 mg/day at time of Aim 2 enrollment. Participants in the control arm will receive a matched placebo. Participants who are found to have symptomatic hypotension and/or new onset /persistent grade 3 (or higher) hyperkalemia after taking study medication (as evaluated at day 3 (safety phone call), week 1, month 1, or during an unscheduled visit will be removed from the study.

Participants who tolerate the initial study dose (5 mg/day or placebo) will be increased to 10 mg/day lisinopril (or matched placebo) at their one (1)-month study visit. All study participants having a dose change/escalation from 5 to 10 mg active medication (or matched placebo), will also (as was done following study enrollment) undergo safety monitoring in the form of a 3-day post dose escalation safety phone call, a 1-week post dose escalation study visit for blood draw/safety evaluation, and 1-month post dose escalation study visit for blood draw/safety evaluation. Those who do not tolerate an increase to the 10 mg/day dose will be returned to the 5 mg/day dose, while those who are able to tolerate an increase to the 10 mg/d dose will be closely monitored for

adverse events and re-assessed (see below) at their 3-month study visit for a possible dose escalation to 20 mg/d of lisinopril.

Participants who tolerate the **10 mg/day lisinopril (or matched placebo) will be increased to 20 mg/day lisinopril** (or matched placebo) at their **three (3)-month study visit**. All study participants having a dose change/escalation from 10 to 20 mg active medication (or matched placebo), will also (as was done following study enrollment and following the 1 month lisinopril dose escalation (from 5 to 10 mg/day)) undergo safety monitoring in the form of a 3 day post dose escalation safety phone call, a 1 week post dose escalation study visit for blood draw/safety evaluation, and a 1 month post dose escalation study visit for blood draw/safety evaluation. Those who do not tolerate an increase to the 20 mg/day dose will be returned to the 10 mg/day dose, while those who are able to tolerate an increase to the 20 mg/day dose will be closely monitored for adverse events and re-assessed (see below) at their 5-month study visit for a possible dose escalation to 40 mg/d of lisinopril.

Participants who tolerate the **20 mg/day lisinopril (or matched placebo) will be increased to 40 mg/day lisinopril** (or matched placebo) at their **five (5)-month study visit**. All study participants having a dose change/escalation from 20 to 40 mg active medication (or matched placebo), will also (as was done following study enrollment and following the 1 month lisinopril dose escalation (from 10 to 20 mg/day)) undergo safety monitoring in the form of a 3 day post dose escalation safety phone call, a 1 week post dose escalation study visit for blood draw/safety evaluation, and a 1 month post dose escalation study visit for blood draw/safety evaluation. Those who do not tolerate an increase to the 40 mg/day dose will be returned to the 20 mg/day dose, while those who are able to tolerate an increase to the 40 mg/day dose will remain at 40 mg/day for the duration of the study. For specifics regarding criteria to be intensively monitored (i.e. blood pressure, serum K+ values, and changes in renal parameters (eGFR and serum creatinine) during all study medication (**Matched Placebo**) **Dose Titration Algorithm**" on pages 25-26 for details.

Alternative medications: Patients who develop side effects to lisinopril (particularly refractory cough) will be transitioned to the equivalent dose of an angiotensin receptor blocker (ARB), losartan, at a dose of 25 or 50 mg/day (depending on the dose of lisinopril (or matched placebo) they were receiving at the time of their adverse event). Most patients that develop a refractory cough on lisinopril (which we believe will be few) if they need anti-hypertensive control will be switched from lisinopril to 50 mg/d of losartan. A few patients may develop a refractory cough very early on study medication (within first 1-2 months of enrollment), and such patients, if they still require antihypertensive medication control may be switched to 25 mg/d of losartan. Patients in need of anti-hypertensive treatment that developed a refractory cough while on study medication will all need to be unblinded due to the severity of this adverse event and most importantly so it can be listed on the patient's active list of medication side effects, so they will not be prescribed ACE inhibitors again in the future. Patients who do not tolerate either study medication (lisinopril or losartan) will be removed from the study and referred to care if needed (see **Figure 2** for details).

Figure 2. Flow diagram of study medication dosing. Endpoints are outlined in green. Symptomatic hypotension will be defined as a reading of lower than 90 mm Hg systolic

or 60 mm Hg diastolic with associated symptoms (i.e. feeling of lightheadedness, weakness) (**NOTE**: All low blood pressure readings will be confirmed, orthostatic blood pressure will be obtained (when clinically indicated/appropriate), and all readings will be put in context of the individual's normal BP readings). Patients removed from the study due to failure to tolerate either the primary (lisinopril) or alternative (losartan) study drug will be unblinded (outlined in **red**) so as to enable their physician to best treat any conditions. (**NOTE**: Hyperkalemia will be graded using established DAIDS Toxicity grading Scale (Version 2.1, July 2017); with grade 1 hyperkalemia = 5.6-5.99 mmol/L, grade 2 hyperkalemia = 6.0-6.49 mmol/L, grade 3 hyperkalemia = 6.5-6.99 mmol/L and grade 4 hyperkalemia (K+ values) being $\geq 7.0 \text{ mmol/L}$).

Nigeria standard of care: The Nigeria HIV/AIDS adult treatment guidelines recommend a baseline assessment of all HIV-positive patients to include a complete history and physical examination, staging of disease with clinical and immunological classification of the patient, and review of laboratory results. In addition, an evaluation of nutritional and psychosocial status, assessment of readiness for therapy, and development of patientspecific adherence strategy is recommended for all patients. All HIV-positive patients, regardless of CD4+ cell count (commonly referred to as the "Test-and-Start" or "Treat All" strategy) are started on ART. First line regimens include: tenofovir (TDF) + lamivudine (3TC) + efavirenz (EFV); TDF + 3TC + nevirapine (NVP); zidovudine (AZT) +3TC (or emtricitabine [FTC]) + EFV and AZT +3TC (or FTC) + NVP. A boosted protease inhibitor plus 2 nucleoside reverse transcriptase inhibitors (NRTIs) are recommended for second-line ART, and available protease inhibitors include ritonavirboosted lopinavir and atazanavir. The government of Nigeria will be transitioning to TLD (tenofovir, lamivudine, plus the integrase strand inhibitor dolutegravir) during 2018-2019. As a result, all HIV positive persons (> 10 years of age and weighing > 30 kilograms) will be switched to TLD during this transition period in accordance with national guidelines/WHO recommendations. In patients with renal insufficiency, i.e. a documented increase in serum creatinine, the guidelines recommend ART regimen dosage modifications if the calculated creatinine clearance (CrCl) is reduced at baseline (i.e. not initiating tenofovir in adult patients having a calculated eGFR of < 50 ml/min/1.73m² or if at any time during follow-up their CrCl decreases significantly (i.e. confirmed to $< 50 \text{ ml/min/1.73m}^2$ from their baseline values). Modifications include switching patients from tenofovir to abacavir as well as investigating potential causes of their worsening renal function (i.e. looking for pre-renal causes such as dehydration, post-renal causes (prostatic obstruction, nephrolithiasis, and/or intra-renal causes such as initiation of new potentially nephrotoxic medications (such as traditional medicines, etc.). Of note, patients switched to dolutegravir (from efavirenz or nevirapine) as part of the soon to commence TLD rollout may also experience a sustained increase in their serum creatinine coupled with a corresponding decrease in their calculated eGFR. In brief, for a period of up to 48 weeks following dolutegravir (DTG) initiation, it is anticipated that study participants may experience a modest (0.2 mg/dL) increase in serum creatinine¹²⁷⁻¹²⁹ that will not lead to significant changes in uACR values but will be lead to aim 2 study participants having a "new baseline eGFR" that is unrelated to study medication and based on the literature using iohexol ¹³⁰ will not represent a true change in eGFR; but nonetheless will still need to be accounted for in the analysis plan. NOTE: Given the known limitations of CysC-based equations for HIV-positive individuals, from an analysis standpoint, the team will utilize/rely on significant changes in serum creatinine (sCr) safety monitoring/reporting among DTG-treated study participants. Patients with reductions in CrCl should undergo an evaluation for potential causes of decreased renal function and have serum creatinine monitored more frequently until

resolution of renal insufficiency or failure. Adjustments to medication dosages should be based on recommendations by drug manufacturers. The national treatment guidelines recommend that routine follow-up assessment of HIV-positive patients should cover: signs/symptoms of HIV-related conditions and potential medication toxicities; adherence; response to therapy; weight; and laboratory monitoring. Every 3 months, the patient should undergo a physical exam and clinical screening for tuberculosis (TB). Every 6 months, the following tests should be performed: CD4+ cell count, hemoglobin (Hgb) and hematocrit (Hct), alanine aminotransferase (ALT), and calculated creatinine clearance (CrCl). Viral load testing is recommended every 6 months. Asparate aminotransferase (AST), alkaline phosphatase (alk phos), fasting blood glucose (FBG), alvcosolated hemoglobin (Hgb A1C), amylase, urine pregnancy testing, lipid profiles (including total/LDL/HDL cholesterol and serum triglyceride levels), serum electrolytes (including sodium, potassium, chloride, bicarbonate, blood urea nitrogen, and creatinine), sputum for acid fast bacilli (AFB) (for TB screening using conventional microscopy and/or GeneXpert MTB/RIF technology), and chest radiography will be performed as clinically indicated.

Longitudinal Study Assessments: All enrolled patients will undergo the following tests at baseline and then every 3 months while on study, until completing 2 years of followup: serum cystatin C, blood pressure, serum electrolytes (creatinine, potassium, sodium, chloride, bicarbonate, and urea), and uACR. Clinical performance status (as measured via the WHOQOL-HIV tool and the Karnofsky performance score) will be evaluated at baseline and at 12 and 24 months. If participant is a female with reproductive potential, she will undergo urine pregnancy testing every 3 months (please see below in **NOTE**). All enrolled aim 2 study participants will have their APOL1 genotype data (i.e. whether HR or LR genotype) available prior to completing study follow-up (see Study Timeline). All patients will undergo routine standard laboratory monitoring as per existing guidelines; specifically, CD4+ cell count and viral load testing (q 6 monthly), liver function test monitoring (at month 1, 3, and 6, and then q 6 monthly following ART initiation), etc., as per Nigeria standard of care (SOC). All enrolled patients will undergo a blood pressure check and have serum electrolytes tested at week 1 and month 1 following study initiation and any changes in dose as part of a brief safety check. All enrolled patients will undergo hepatitis B and C screening at baseline. Additional funds have been allocated for patients to undergo unscheduled safety monitoring (up to two additional times per year) as needed, while on study.

NOTE: Females with reproductive potential will receive extensive education regarding the risks of ACEi therapy; namely the potential risk of congenital abnormalities during the first trimester (one study¹³¹) as well as the documented increased risk of fetal renal damage in the 2nd and 3rd trimesters.¹³² All reproductive-aged females will undergo preenrolment and q 3-monthly urine pregnancy testing and, if they test positive, they will be immediately unblinded and their study medication (if on active study medication; i.e. lisinopril) will be discontinued immediately and an appropriate substitution will be made if needed (i.e. anti-hypertensive).^{131,132} We will also educate all enrolled women having reproductive potential to immediately report to the study staff if they suspect being pregnant. If they do suspect being pregnant, they will immediately report to the research team, their ACEi will be discontinued, and they will undergo the necessary evaluations (i.e. urine pregnancy testing) with alternative anti-hypertensive medications being prescribed as needed among women confirmed as being pregnant. **Study medication and adherence:** The medication or placebo will be provided to each study participant at no cost to the participant. Study medications will be stored at the clinical site in a locked storage cabinet that will be accessible to the study pharmacist and site PI. The study pharmacist will ensure the medicine is stored properly and dispensed only when needed for study participants. The site investigators will assure the medicine is stored properly and dispensed only when need for study participants to by the clinical pharmacist designated at the clinical site. The following will be monitored and completed on a continuous basis to assure the medicine is within study guidelines, onsite pharmaceutical compliance, and manufacturer guidelines:

- 1. Delivery Log of Medication
- 2. Drug Accountability Record
- 3. Drug Safety and Handling Sheet

We will ascertain adherence to study medication via self-report, medication possession ratio (using pharmacy prescription/dispensing data),¹³³ and by measuring change in blood pressure (post hoc) among patients randomized to the intervention (ACEi) arm. We will also measure adherence using a modified version of the brief medication questionnaire (BMQ)¹³⁴ every six months, and the score will be shared with the patient during this visit (i.e., high, average, or poor adherence). Using evidence-based strategies,²²⁻²⁴ we will implement educational and behavioral interventions that have proven successful in other studies for persons categorized as having poor adherence (≥ 1 points). For persons demonstrating average to high adherence (<1 point), we will implement positive reinforcement with the continuation of educational interventions throughout the study.^{21,23}

Randomization procedures (including assignment of randomized participants into 6 (six) strata based on uACR and *APOL1* risk allele genotype:

The randomization process will be a stratified randomization with varied block sizes and random block sequences. The stratified randomization addresses the need to balance the baseline uACR values and high-risk genotypes among the intervention and control groups. Enrolled patients will be stratified into six groups by uACR values and number of high risk alleles of range 30-59 + 2 high risk alleles, 30-59 + 1 high risk allele, 30-59 + 0 high risk alleles, 60-300 + 2 high risk alleles, 60-300 + 1 high risk allele, and 60-300 + 0 high risk alleles, and the six groups will have approximately 35, 35, 70, 35, 35, and 70 patients respectively. These six strata are determined to make sure that the study arms are well-balanced and that we will have enough participants with high risk genotypes to be able to complete Aim 3 of the study. This decision tries to find a balance between recommendations to keep the number of strata as small as possible (3 to 4 strata is generally advisable with an average of 50-100 patients per stratum)¹³⁵ while ensuring that we have adequate numbers of persons with high risk genotypes. Relatively small block sizes of 2, 4, and 6 will be used in order to ensure balanced group sizes among the two arms over time. To make the allocation of participants unpredictable, the sequence of blocks will also be randomized. Three series of randomly ordered letters of "A" and "B" will be generated using R software. The blockrand package of R will be used to generate random treatment assignment using the block design described above. To ensure there are enough random assignments for each group, we will generate lists of size 50, 50, 100, 50, 50, and 100 for the 6 strata.

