Teratogenicity (Pregnancy Considerations): Lisinopril has been found to be teratogenic in mice and therefore is classified as class D by the FDA. All women of childbearing age (and potential) in this study will be extensively counseled about these potential risks and will be linked to family planning/spacing services, if desired. They will also undergo urine pregnancy testing at the beginning of the study and every three months at no cost. Any participant found to be pregnant will be withdrawn from the study. In addition, all women of childbearing age (and potential) will be extensively counseled and told to come immediately to clinic if they suspect for any reason that they may have become pregnant; i.e. missed/delayed menses, unexpected weight gain, etc.

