7.0 Study Withdrawal/Discontinuation

Participants may decide to discontinue participation at any time during the study. If a patient voluntarily requests withdrawal from the trial, we request that the site investigator

elicit the reason for the withdrawal and provide documentation in the clinic record and complete the respective case report form. We will have a dedicated patient navigator on staff as well to help trace and re-engage all participants lost to follow-up, realizing that some may die or transfer their care and must be appropriately categorized. Those who drop out due to AEs or perceived AEs will be counseled by study physicians regarding their options and any potential risks for continuation. The site must invest time in trying to meet the needs of the patient and their caregivers in order to make the patient's participation a success. The patient's caregiver should provide the withdrawal in writing for the clinic record. All voluntary withdrawals must be communicated to the SOC located at Vanderbilt University Medical Center by completion of the case report form in REDCap and should be recorded in the participant's study binder onsite.

Principal Investigator-initiated Withdrawal

Investigators may discontinue any participant at their discretion, if in their professional opinion the participant's health, safety, and/or well-being is being threatened or at all jeopardized by continued participation in the study. The following circumstances require discontinuation of participants:

- 1. Withdrawal of assent to participate;
- 2. Parental withdrawal of consent to participate;
- 3. Study physician determines that continuation in the study would not be in the best interest of the participant, e.g., pregnancy;
- 4. Participant has experienced a serious and/or unanticipated adverse event.

Adverse events caused by participation in the study may necessitate modifications to the level of participation of a subject or discontinuation of participation in the study. Participants who discontinue early from the study will not be replaced. They will continue to receive medical care at the AKTH HIV clinic as per standard care.

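### Participants who cannot take study drug are taken out of the study, so the intention-to-treat uACR comparison risks informative censoring

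*Combined protocol and SAP*

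**What the plan says.** Three rules end study participation, not only dosing:

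- Section 5.0, Aim 2 Study Medication: participants with symptomatic hypotension, or with new or persistent grade 3 or higher hyperkalaemia, at day 3, "week 1, month 1, or during an unscheduled visit will be removed from the study".
- Section 5.0, Alternative medications: "Patients who do not tolerate either study medication (lisinopril or losartan) will be removed from the study".
- Section 6.0, Teratogenicity: "Any participant found to be pregnant will be withdrawn from the study".

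Section 7.0 goes further if read literally. Under "The following circumstances require discontinuation of participants" it lists "Participant has experienced a serious and/or unanticipated adverse event". That list may be template text, since it also includes "Parental withdrawal of consent to participate" in a trial of adults.

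On follow-up, Section 5.0 (Longitudinal Study Assessments) schedules uACR at baseline and "every 3 months while on study, until completing 2 years of followup". Of those who discontinue early, Section 7.0 says "They will continue to receive medical care at the AKTH HIV clinic as per standard care". The six-monthly tests listed under Nigeria standard of care do not include uACR. After drug is stopped, Section 6.0 describes only adverse event and pregnancy information.

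Other places point the other way. Section 1.2 (Secondary Endpoints) and Section 9.0 plan two years of follow-up for all. The dose titration table and the text on allergic reactions and worsening renal function describe holding, reducing, stopping or resuming drug. The pregnancy note in Section 5.0 and the pregnancy reporting text in Section 6.0 describe only unblinding and stopping drug.

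**The concern.** Section 8.0 (Specific Aim 2) makes intention to treat the primary analysis, with Cox models for regression and progression and a linear mixed model for uACR. That analysis needs uACR values after drug is stopped. Hypotension, hyperkalaemia and intolerance are expected effects of lisinopril, so removals may be more frequent on active drug. Pregnancy has no clear reason to differ by arm, but its removal still loses data.

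The Cox models need censoring to be non-informative. The mixed model needs later values to be missing at random given the earlier ones. Early removals are the hardest case. Week 1 and month 1 safety visits list blood pressure and electrolytes, and the first scheduled uACR after baseline is at month 3. A participant removed before then has only a baseline uACR, which the models use as a covariate. That person contributes no uACR outcome and in effect leaves the randomised comparison. The plan states no missing-data method or censoring rule for removals. The only sensitivity analyses it names concern the switch to dolutegravir.

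**Working it through.** **Does uACR follow-up end at removal?** No sentence says so outright, so this is an inference. Four points support it: uACR visits are tied to being on study; Section 6.0 says that participants who switch to losartan stay on study, so the protocol separates changing drug from leaving; the Aim 2 sample size text uses the same term for those still followed; and those who discontinue go to standard care, whose listed routine tests omit uACR.

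**The plan's own figure.** Section 8.0, Table 3 (power for regression) gives 0.828 for 140 per arm, alpha 0.017, hazard ratio 2.5 and 12% regression on standard of care. After 10% loss, events = 126 × (0.12 + 0.30) = 52.9, or 53. By Schoenfeld's formula, power = Φ(ln 2.5 × √53 / 2 − 2.387) = 0.829. It reproduces.

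**Assumptions for the size of the effect.** The removal share p is not in the documents. I take p = 2, 5 and 10% of the 140 on lisinopril (about 3, 7 and 14 people). The top value equals the plan's whole loss allowance and serves only as a ceiling. Removed participants are assumed to return fully to the placebo level and otherwise to resemble those who stay. Placebo removals then add no bias.

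*Mean log uACR.* Section 1.2 expects a 40% fall against a 10% rise: ln(0.60/1.10) = −0.606. As randomised, the difference is (1 − p) × 0.606, so each 1% removed overstates it by 0.006 (0.003 if participants return halfway).

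*Regression.* With exponential times and 12% on placebo, cumulative hazard = −ln(0.88) = 0.1278. Lisinopril risk = 1 − exp(−2.5 × 0.1278) = 0.2735. At p = 5%, the as-randomised risk is 0.95 × 0.2735 + 0.05 × 0.12 = 0.2659, and the hazard ratio is −ln(1 − 0.2659) / 0.1278 = 2.42.

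*Progression.* With 60% on placebo, cumulative hazard = 0.9163 and lisinopril risk at hazard ratio 0.42 = 0.3194. At p = 5%, the as-randomised risk is 0.333 and the hazard ratio 0.44.

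| Lisinopril arm removed | Log-uACR difference | Regression hazard ratio | Progression hazard ratio |
|---|---|---|---|
| 0% (also what is seen if data stop at removal) | 0.606 | 2.50 | 0.42 |
| 2% | 0.594 | 2.47 | 0.43 |
| 5% | 0.576 | 2.42 | 0.44 |
| 10% | 0.546 | 2.34 | 0.47 |

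**Does the mixed model recover the loss?** Not under this assumption. A random-intercept model was simulated with 20,000 per arm, baseline as covariate and a month-24 contrast. With 5% removed at month 1, it gave −0.608 when data stop at removal and −0.577 with full follow-up. With 5% removed after month 6, it gave −0.601 and −0.571. Values before removal are on-drug values, so they do not reveal the later return to the placebo level.

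**Tipping point.** The difference falls to the plan's detectable 0.24 when p = 1 − 0.24/0.606 = 60%, about 85 of 140.

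**Power for regression if everyone is followed** (alpha 0.05/3, 126 per arm, plan rates 12% and 30%). At 5% removed, events = 126 × (0.12 + 0.95 × 0.30 + 0.05 × 0.12) = 51.8 and the hazard ratio is 2.42, giving power 0.78. Stopping data at removal leaves 51.0 events at hazard ratio 2.50, giving 0.81. At 10% the figures are 0.73 and 0.79.

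**The case against.** The strongest reply is that this is inconsistent wording, not a design that ends follow-up. The dose titration table stops study medication at any potassium above 6.0, and grade 3 starts at 6.5, so every removal-level potassium is already covered by a drug-only rule. Just after its list, Section 7.0 says that adverse events may lead to a changed level of participation, which is discretionary. The dosing flow diagram, to which Section 5.0 refers for details of removal, cannot be seen in the text available. All of this stands as reason for caution about what sites would do. It does not remove the three explicit rules. A site that follows either reading would be compliant, and missed uACR visits cannot be recovered. The patient navigator in Section 7.0 traces those lost to follow-up, not those whom the protocol removes.

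The triggers are also narrow. Entry excludes potassium above 5.0 and persistent symptomatic hypotension, failed dose steps go back one dose, and losartan switchers stay. The removal rate may therefore be low and the effect small, and this too stands.

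Finally, the power figures take the diluted hazard ratio from a 27.4% lisinopril risk but count events at the plan's 30%. Using 27.4% throughout gives 0.797 with no removal, 0.753 against 0.781 at 5%, and 0.70 against 0.76 at 10%. The level is lower, but the gap between the two options is about the same.

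**Conclusion.** The concern holds, as a risk and not as a demonstrated bias. Followed as written, the removal rules take participants with lisinopril-related events out of an intention-to-treat comparison whose primary endpoints are all uACR outcomes. With 2 to 10% of the lisinopril arm removed and a full return to the placebo level, the log-uACR difference would be overstated by 0.012 to 0.061, or half that with a half return. The hazard ratios would move by at most 0.16 (regression) and 0.05 (progression). The likely harm is to the size of the estimate, not to the conclusion. The direction could differ if removed participants have a worse renal course. Confidence is medium, because the removal rate is unknown and the end of uACR follow-up is inferred. It should be fixed because the remedy is cheap and lost visits cannot be recovered.

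**What to change.** Define discontinuing study medication separately from withdrawing from the study. Participants who stop drug for an adverse event, serious adverse event, intolerance or pregnancy should stay on the 3-monthly uACR, creatinine and cystatin C schedule to month 24 unless they withdraw consent, and be analysed as randomised. Delete the serious or unanticipated adverse event item in Section 7.0 as a reason to end follow-up. Reconcile the removal, pregnancy, allergy, titration and renal-management text in Sections 5.0, 6.0 and 7.0. Leave the drug-stopping and unblinding rules as they are. Add a sensitivity analysis for those who still leave, and state how uACR values during pregnancy are handled, since the Background links microalbuminuria to preeclampsia.

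The cost is protocol wording plus visits already planned. Some follow-up will be off drug or unblinded, and some participants may start other treatment. The observed effect may be smaller: power for regression would be about 0.78 instead of 0.81 at 5% removed, and 0.73 instead of 0.79 at 10%. The higher figures come from leaving out participants whom intention to treat is meant to include.
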